6.8 Handling of Partial Dates for Procedures

For records with a missing procedure date, the following procedure will be employed to determine whether the procedure is prior or concomitant:

- For a procedure with a missing or partially missing date performed on a scheduled visit, the date of the scheduled visit will be used.
- If a procedure was not scheduled, the missing part of the date will be imputed as discussed in Section 6.9.

6.9 Handling of Partial Dates for Other Data

Other data (such as disease history) with partial dates will be listed as collected. For calculation of time intervals, the dates will be imputed with the first day of the month (if the day is missing) or with 1 January (if both day and month are missing).

6.10 Handling of Missing Data

Missing data will not be imputed, except for:

- Missing date parts, i.e., partial dates, discussed above
- Missing AEs grade severity and relationship to study drug of AEs, discussed in Section 8.6.2.
- Missing efficacy assessments discussed in Section 8.7.

Confidential Page 15 of 30

7 ANALYSIS SETS

The following analysis sets will be used for analysis of Phase 2 data:

7.1 All Subjects Analysis Set

All Subjects Analysis Set includes all subjects who signed informed consent form, irrespective if they passed or failed screening for Inclusion and Exclusion criteria. This set will be used for listing of all subjects who received study treatment and all subjects excluded from the study during the screening period due to failure to meet eligibility criteria.

7.2 Safety Analysis Set

Safety analysis set includes all subjects who received at least one dose of study drug. This set is considered as a Full Analysis Set that will be used for both safety and efficacy analysis.

7.3 Efficacy Analysis Set

Efficacy analysis set includes subjects who have received ≥2 doses of study drug. Efficacy analysis on efficacy analysis set will be performed as a sensitivity analysis.

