6.4.2 Efficacy Analysis

Efficacy endpoints will be measured in the safety analysis set. As an exploratory analysis, similar calculations will be performed on the efficacy analysis set.

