8.7 Efficacy Analysis

All efficacy analyses will be performed based on the Safety Analysis Set and the Efficacy Analysis Set.

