8.7.6 Progression-Free Survival

Progression-free survival (PFS) is defined as the interval from the date of first dose of investigational agent until the earliest date of PD per RECIST 1.1 or death due to any cause within 90 days (i.e., 12 weeks+6 days) of last tumor assessment (if no progression is documented). If a patient transitioned to a new anti-cancer therapy, any time point assessment(s) and death(s) that happened after that will be disregarded.

The primary analysis will be performed ignoring transient PDs, using the same definition of transient PDs as in Section 8.7.1. Thus, the terminating event will be a non-transient PD or death, whichever occurs first. Patients who did not experience a non-transient PD or death will be censored on the date of last evaluable tumor assessment, the date of the last evaluable assessment without any assessment in the following 90 days and then followed by PD or death, or the last evaluable assessment performed before initiation of new anti-cancer therapy (if applicable), whichever comes earlier.

The alternative (sensitivity) analysis will be performed for terminating event of death or first observed time-point PD, whichever occurs first. Censoring will be on the date of last evaluable tumor assessment, the date of the last evaluable assessment without any assessment in the following 90 days and then followed by PD or death, or the last evaluable assessment performed before initiation of new anti-cancer therapy (if applicable), whichever occurs first.

PFS will be reported in months. Median PFS will be provided (estimated using K-M estimate, with 95% CI) and Kaplan-Meier curves of PFS will be plotted.

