8.7.7 Overall Survival

Overall survival (OS) is defined as the interval from the date of first dose of investigational agent until the date of death.

OS in months is calculated as:

- (date of death, or censoring date of first dosing + 1) / 30.4375
- Where the censoring rules are specified as following:
- For subjects who have not died, OS will be censored at last contact date.
- Median OS will be provided (estimated using K-M estimate, with 95% CI) and Kaplan-Meier curve of OS will be plotted for Safety Analysis Set.

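### PFS and OS are repeated in subjects selected for a second dose but still timed from the first dose, which builds in about 3 weeks of guaranteed survival and an expected upward bias

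*SAP*

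**What the plan says.** - **Selection.** SAP 7.3: "Efficacy analysis set includes subjects who have received ≥2 doses of study drug". Protocol 6.3 has the same rule and adds that the doses be at the assigned level.
- **Label.** SAP 7.3: "Efficacy analysis on efficacy analysis set will be performed as a sensitivity analysis". Protocol 6.4.2 ranks it lower: "As an exploratory analysis, similar calculations will be performed on the efficacy analysis set". SAP 5.1 records no change from the protocol.
- **Scope.** SAP 8.7: "All efficacy analyses will be performed based on the Safety Analysis Set and the Efficacy Analysis Set". Read literally, that includes PFS and OS.
- **Clock.** SAP 8.7.6 defines PFS as "the interval from the date of first dose of investigational agent until the earliest date of PD per RECIST 1.1" or death. SAP 8.7.7: "Overall survival (OS) is defined as the interval from the date of first dose of investigational agent". Neither section gives a landmark, a second-dose origin or delayed entry for the two-dose set.
- **Main population.** SAP 7.2, on the Safety Analysis Set (at least one dose): "This set is considered as a Full Analysis Set that will be used for both safety and efficacy analysis".
- **Loose end.** SAP 8.7.7 ends: "Kaplan-Meier curve of OS will be plotted for Safety Analysis Set". It does not mention the Efficacy Analysis Set, which sits awkwardly with SAP 8.7.

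**The concern.** Receiving a second dose is a post-baseline event, and a subject must be alive to receive it. A subject who dies before then is an OS event in the Safety Analysis Set and is absent from the Efficacy Analysis Set. With the clock started at the first dose, everyone in the Efficacy Analysis Set is immortal up to the second dose. Until then its OS curve cannot lie below that of the Safety Analysis Set.

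A sensitivity analysis is meant to show whether the main result survives a reasonable change of assumption. A result at least as good in this set would look like confirmation, although part of it comes from how the set was chosen. PFS and OS are also summarised by subgroup (SAP 8.7.5), including about 20 HCC subjects, where one or two early deaths matter.

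**Working it through.** The plan gives no median, event count or power figure to reproduce; SAP 3.2 says the sample size has no inferential basis. All survival medians below are therefore assumptions, shown over a range.

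**Inputs from the documents.** Dosing is every 3 weeks for the first 4 cycles (Protocol 4.1.1), with a window of 3 days either side for Cycle 2 Day 1 (Protocol Table 10). One month is 30.4375 days (SAP 8.1). Phase 2 enrols up to 60 subjects (SAP 3.2). The first scheduled scan is at Week 6 (Protocol 5.7.1).

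**Step 1: guaranteed survival.** 21 / 30.4375 = 0.69 month. For 18 to 24 days the range is 0.59 to 0.79 month.

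**Step 2: size if early death is the only reason for exclusion.** With exponential OS and median m months, P(death before day 21) = 1 − 2^(−0.69/m). The median in the two-dose set, timed from the first dose, is m + 0.69. Survival at a later time t is S(t) / [1 − P(death before day 21)].

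| Assumed m (months) | Die before day 21 | Of 60 | Median in two-dose set | 6-month OS, Safety → Efficacy Set | 12-month OS, Safety → Efficacy Set |
|---|---|---|---|---|---|
| 3 | 14.7% | 8.8 | 3.69 | 25.0% → 29.3% | 6.2% → 7.3% |
| 6 | 7.7% | 4.6 | 6.69 | 50.0% → 54.1% | 25.0% → 27.1% |
| 12 | 3.9% | 2.3 | 12.69 | 70.7% → 73.6% | 50.0% → 52.0% |
| 18 | 2.6% | 1.6 | 18.69 | 79.4% → 81.5% | 63.0% → 64.7% |

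**Step 3: general form and upper bound.** Let p be the share who receive a second dose, and a the share of the excluded who are alive at t. Then survival in the two-dose set is [S(t) − (1 − p)a] / p. Setting a = 0 gives S(t)/p, the largest value possible. For an assumed 3-month OS of 70%:
- Upper bounds: 0.70/0.95 = 74%; 0.70/0.90 = 78%; 0.70/0.85 = 82%.
- p = 0.90 and a = 0.70: (0.70 − 0.07)/0.90 = 70%, no change.
- p = 0.90 and a = 0.90: (0.70 − 0.09)/0.90 = 68%, lower.

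Under a constant hazard, 70% at 3 months implies about 8% dying before day 21, which gives about 76%. The 82% case would place half of all 3-month deaths (15 of 30 percentage points) before the second dose.

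**Step 4: can the direction reverse?** Suppose a share q of those alive on day 21 stop after one dose, with residual median r × m, while the others keep residual median m. The Efficacy Set median stays at m + 0.69. Safety Set survival is 2^(−0.69/m) × [(1 − q) × 2^(−(t − 0.69)/m) + q × 2^(−(t − 0.69)/(r × m))].

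| m | q | r | Median, Safety Set | Median, Efficacy Set |
|---|---|---|---|---|
| 12 | 10% | 1 | 12.0 | 12.7 |
| 12 | 10% | 4 | 13.2 | 12.7 |
| 12 | 20% | 2 | 13.5 | 12.7 |
| 6 | 20% | 4 | 7.2 | 6.7 |

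In the third row 24-month OS is 29.8% in the Safety Set and 26.0% in the Efficacy Set. Even with equal prognosis (q = 10%, r = 1) and 60 subjects, the Efficacy Set median was the lower one in about 6% (m = 6) to 17% (m = 12) of simulated trials.

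**Step 5: PFS.** A second dose shows that the subject was alive, not progression-free: Protocol 3.7 allows dosing beyond progression. As the first scheduled scan follows the nominal second dose, few progressions would be recorded before it in either set. The PFS effect therefore runs mainly through early deaths, and the 0.69-month shift in Step 2 applies to OS only.

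**The case against.** The strongest reply is that nothing important rests on this analysis. The main efficacy population is every treated subject (Protocol 6.4.2, SAP 7.2), the protocol calls the repeat exploratory, and there is no test, threshold or comparator. The 12-week life-expectancy criterion (Protocol 3.2.1) limits early deaths. SAP 8.2 and 8.3 already report the size of each set, list membership and tabulate reasons for discontinuation, so exclusions can be traced. SAP 8.7.7 names only the Safety Analysis Set for the OS curve, so OS in the second set rests on the general sentence in SAP 8.7. All of this stands, and it keeps the point minor. None of it supplies a landmark or makes the repeat a robustness check.

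A reader might also infer that results in this set can only look better. The documents do not support that. Subjects can be stopped permanently for adverse drug reactions (Protocol 4.4.2) and are still followed for survival (Protocol 5.1.5), so the set drops living subjects as well as early deaths, and Step 4 shows the direction can reverse. Nor should S(t)/p be read as the expected effect, because stopping after one dose is not an OS event. Nor is every member guaranteed to be progression-free up to the second dose.

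**Conclusion.** The concern holds as a minor point. Selecting on a second dose while timing from the first gives about 3 weeks (0.69 month) of guaranteed survival. OS in this set, and PFS mainly through early deaths, is expected to be biased upward.

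For OS the size is about 0.7 month on the median, and about 2 to 4 percentage points on survival at the median time for assumed medians of 12 and 6 months. This assumes exponential survival, a second dose on day 21, and exclusion by early death only. If living one-dose subjects do well, the bias shrinks or reverses. The documents give no survival medians and no expected share of one-dose subjects, so the actual size is unknown. It would be wrong to infer that the trial's main efficacy results are biased; they rest on the Safety Analysis Set. What fails is the use of this analysis as a sensitivity check for PFS and OS.

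**What to change.** **Preferred.** In SAP 7.3 and 8.7, limit the Efficacy Analysis Set to response summaries and report PFS and OS only in the Safety Analysis Set. This also reconciles SAP 8.7 with the OS wording in 8.7.7. The cost is a short SAP edit and the loss of one exploratory analysis; no new data are needed.

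**Alternative, if PFS and OS are kept in this set.** Start both at the second-dose date in SAP 8.7.6 and 8.7.7, label the result exploratory (as in Protocol 6.4.2) and conditional on receiving a second dose, and reconcile 8.7 with 8.7.7. In the exponential case this returns the median from 6.69 to 6.00, or from 12.69 to 12.00 months. It departs from the first-dose origin in Protocol 6.2.1.2 and SAP 4.5, so it needs an entry in SAP 5.1. Medians would then not be directly comparable between the two sets.

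Either way, state next to any result from this set how many one-dose subjects were excluded and why.

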8 STATISTICAL CONSIDERATIONS

All analyses described in this plan are considered a priori analyses as they have been defined prior to database availability for analysis. The COVID-19 pandemic may impact Agenus ability to complete data monitoring, collection, and cleaning to achieve the data lock as originally planned for our clinical programs. As a result, a priori analysis of Agenus clinical trial data may be completed prior to all data locked; however, all analysis will occur using locked and frozen clinical database records and ensuring trial data integrity is maintained as locked or frozen on the subject and visit levels. Clinical data management will notify the team when data are available (all locked or frozen) for download and the planned analysis. The impact of lack of source data verification or principal investigator (PI) signature will be performed at the time of data download. Only significant impact/risks to analysis of data, with the planned mitigation, will be discussed in the clinical study report (CSR). Clinical data management will post queries requesting data changes after the data download for the analysis, result of completion of Source Data Verification (SDV) or new information provided. Requested changes will be reviewed by the team before changes are made to the database by the sites. An additional analysis may be performed if data changes would affect study conclusions; additional analysis will be described in the applicable SAP. All other analyses, if any, designed after completing analysis specified in

Confidential Page 16 of 30

this SAP and additional analysis plans referred by the SAP, will be considered post-hoc analyses and will be described in a separate exploratory analysis plan (if applicable).

All summaries and statistical analysis will be performed using SAS Software (SAS Institute Inc., Cary, NC, USA), version 9.4 or later, or R (R Foundation for Statistical Computing, Vienna, Austria), version 3.6.3 or later.

8.1 General Statistical Procedures

Frequency distributions for categorical variables will be provided as number of subjects in the category and the percentages of the total number of subjects in the given population as noted. Counts of missing observations will be included in the denominator and presented as a separate category. Percentages will be reported to one decimal place.

A 2-sided 95% Wilson score confidence interval (CI) for categorical variables without multiplicity adjustment will be provided where appropriate for efficacy analysis.

The descriptive statistics for continuous variables will be number of subjects, mean, standard deviation, median, minimum, and maximum. Mean and median will be reported to 1 more decimal place than the raw data, while the standard deviation will be reported to 2 more decimal places than the raw data. Minimum and maximum will be reported the same as the original data.

All listings (with the exception of All Subject listings) will be performed using the Safety Analysis Set and sorted by subject ID and, if applicable, by visit date unless otherwise specified.

The study drug name may be abbreviated in TLFs as "Zal" for zalifrelimab (AGEN1884).

Time intervals (in days), unless specified otherwise, will be calculated as difference between ending and start day + 1 day. For conversion to months, interval days will be divided by 30.4375.

8.2 Subject Enrollment

The number of subjects in each analysis set will be summarized. In addition, a listing will be provided for All Subjects Analysis Set, including informed consent date, screening status (screen failure/enrolled), date of first dose, and analysis sets membership (Yes/No).

8.3 Subjects Disposition

Subject disposition will be summarized including

- Number of subjects treated
- Number of subjects who completed study treatment as per protocol
- Number of subjects who discontinued treatment and primary reasons of discontinuation
- Number of subjects who completed the study as per protocol
- Number of subjects who discontinued study and primary reasons of discontinuation

The Safety Analysis Set and the Efficacy analysis Set will be applied to summary tables. Subject disposition will be listed.

8.4 Protocol Deviations

Protocol deviations will be reviewed by study team to designate important protocol deviations. These important protocol deviations will be summarized by category, and all protocol deviations will be listed for the Safety Analysis Set.

8.5 Demographics and Baseline Characteristics

8.5.1 Demographic and Baseline Characteristics

Demographic and baseline characteristics will be tabulated using descriptive statistics in both the Safety Analysis Set and the Efficacy Analysis Set. The following variables will be included:

- Age at screening (years)
- Age category (age < 55 vs age ≥ 55 , age < 65 vs age ≥ 65 , age < 75 vs age ≥ 75)
- Race
- Ethnicity
- Height (cm)
- Weight (kg)
- BMI (body mass index, kg/m²), defined as weight (kg) / height (m)²
- Eastern Cooperative Oncology Group (ECOG) performance status
- Tumor type

Demographics and baseline characteristics will be listed.

8.5.2 Medical History

Medical history will be coded using the Medical Dictionary for Regulatory Activities (MedDRA) version 22.1.

Conditions and symptoms that were ongoing at baseline will be summarized. Previous medical history data will be summarized separately as "medical history".

The frequency count and percentage of subjects experiencing any medical conditions will be tabulated by system organ classifications (SOC) and preferred term (PT). If a PT or SOC was reported more than once for a subject, the subject would only be counted once in the incidence for that PT or SOC.

The Safety Analysis Set will be applied for this analysis.

Confidential Page 18 of 30

8.5.3 Cancer History

Subjects' cancer history prior to study entry will be summarized, including:

- Status at diagnosis
- The number of subjects with HCC, non-HCC and PD-1/PD-L1 refractory, or non-HCC and PD-1/PD-L1 naïve
- Time from original diagnosis to first dose date (years), calculated as (first dose date initial diagnosis date)/365.25
- Current cancer diagnosis
- Localization of metastases (lymph nodes vs other [i.e., all non-lymph nodes])
- Tumor burden (sum of baseline target lesions) using descriptive statistics and frequency ≤ 50 mm vs > 50 mm.

A listing of prior anti-cancer treatment will be provided to the sponsor for review for the purpose of determining if patients are PD-1/PD-L1 refractory or naïve. Individual cancer history will be listed.

The Safety Analysis Set will be applied for this analysis.

8.5.4 Prior Cancer Therapies and Procedures

Prior cancer systemic therapies will be summarized and listed including:

- Any prior cancer medication
- BOR on the last treatment/therapy before enrollment
- Time from last day of last treatment to first dose date (months), defined as (first dose date date of last day of last treatment + 1)/30.4375

Anti-cancer therapies will be coded using WHODrug-B3 September 2019. Prior anti-cancer treatment, radiotherapies, and surgeries will be listed.

The Safety Analysis Set will be applied for this analysis.

8.5.5 Prior and Concomitant Medications

Prior and concomitant medications will be summarized and listed in the Safety Analysis Set. Medications will be coded using WHODrug-B3 September 2019. The count and percentage of subjects who took concomitant medications will be tabulated by Anatomical Therapeutic Chemical (ATC) level 2 and PT. Prior medication is defined as any non-study medication started before the first dose of study drug. Concomitant medication is defined as any non-study medication that was dosed on or after first study drug administration.

Confidential Page 19 of 30

Agenus Inc. Statistical Analysis Plan for Study C-500-01 Phase 2

A prior medication could also be classified as "both prior and concomitant medication" if the end date is on or after first dose of study drug. In the listing, it will be indicated whether a medication is prior-only, concomitant-only, or both prior and concomitant medication.

The Safety Analysis Set will be applied for this analysis.

8.6 Safety Analysis

The Safety Analysis Set will be applied for all safety analyses.

8.6.1 Drug Exposure

Overall drug exposure will be summarized in Safety Analysis Set by the following parameters:

- Duration of treatment (week), calculated as: (last dose date first dose date + 1)/7
- Number of treatment infusions received
- Total cumulative dose (mg), defined as the sum of the actual doses (mg) taken
- Dose compliance, defined as percentage of actual dose taken relative to planned dose
- Planned/actual dose intensity for the first 4 cycles, defined as total planned or actual dose from the first 4 cycles (mg) divided by actual duration of the first 4 cycles (weeks)

Note: if patients permanently withdraw from the treatment before Cycle 4 due to reasons other than disease progression or death, the remaining cycles will be calculated with planned length, i.e., 3 weeks, and zero dose. If patients withdraw from the treatment due to disease progression or death, the number of cycles actually completed will be used.

- Number of doses with infusion related reactions (as reported on drug administration eCRFs)
- Number of subjects with at least one infusion related reaction
- Number of subjects with any dose interrupted/not completed
- Number of doses interrupted/not completed
- Occurrences and number of actual doses exceeding adjusted planned dose by more than 5% (adjusting for up to 10 % weight loss.)

Per pharmacy manual, no adjustment in dose was required for body weight changes within 10%, therefore dose exceeding planned dose by > 5% will be interpreted as any dose 5% greater than the highest daily dose prescribed by the clinical trial protocol, after accounting for up to 10% changes due to decrease in body weight. Adjusted planned dose is calculated by multiplying prescribed dose level by adjusted weight W_{adj} . Denoting by W_0 and W_{adj} the baseline and the most recent weights, adjusted weight is: $W_{adj} = W$ for $W \ge W_0$ and $W_{adj} = \min(W_0, 1.1 \times W)$ for $W < W_0$.

Missing weight measurements in drug exposure analysis will be imputed by last observation carried forward, multiple measurements for the same timepoint will be averaged.

Confidential Page 20 of 30

Details of study treatment exposure will be listed for Safety Analysis Set.

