4.1.2 Dosing Delay Criteria

Prior to every AGEN1884 administration, laboratory values will be reviewed. AGEN1884 administration will be delayed for the following adverse events (AEs), if the following AEs occur on the day of planned AGEN1884 dosing:

- Either febrile neutropenia or neutropenia <500 cells/mm³ for >1 week despite the use of growth factors.
- Any grade ≥2, non-skin, drug-related AE except for fatigue and laboratory abnormalities
- Any grade 3 drug-related laboratory abnormality (except lymphopenia, AST, ALT, total bilirubin, or asymptomatic lipase or amylase).
 - o Grade 3 lymphopenia does not require a dose delay.
 - o If the subject has a baseline AST, ALT, or total bilirubin that is within normal limits, dosing should be delayed for drug-related grade ≥2 toxicity.
 - o If the subject has a baseline AST, ALT, or total bilirubin within the grade 1 toxicity range, dosing should be delayed for drug-related grade ≥3 toxicity.
 - o Any grade 3 drug-related amylase or lipase abnormality that is not associated with symptoms or clinical manifestations of pancreatitis does not require dose delay.
- Any grade 3, skin, drug-related AE.
- Any AE, laboratory abnormality, or intercurrent illness that, in the judgment of the investigator, warrants delaying the dose of study medication.
- For subjects in Phase 2 with HCC and an elevated baseline liver function test:

Dose delay for the following:

- Baseline AST, ALT \leq 2 x ULN with an increase to \geq 5 x ULN
- Baseline AST, ALT ≥ 2 x ULN with an increase to ≥ 3 x the baseline level
- Elevations of AST, ALT ≥500 IU/L or 20 x ULN regardless of baseline level
- Baseline total bilirubin ≤ 1.5 x ULN and increase to ≥ 2 x ULN
- Baseline total bilirubin >1.5 x ULN and increase to \geq 2 x baseline level
- Elevations of total bilirubin $\ge 3x$ ULN regardless of baseline level

Permanently discontinue for

- Elevations of ALT ≥20 x ULN regardless of baseline level
- Clinical Hepatic Decompensation regardless of lab values as follows:
 - New onset clinical ascites
 - Upper gastrointestinal bleeding due to portal hypertension
 - o Encephalopathy
 - Coagulopathy due to liver disease
 - Worsening Child-Pugh score to 9

Confidential Page 34 of 78

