4.4.1 Dose Reductions

No dose reductions are allowed. Each subject will stay on the regimen dose levels assigned in the trial unless treatment needs to be stopped. Dose reductions or dose escalations of AGEN1884 are not permitted.

Confidential Page 45 of 78

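### SAP 8.6.1 divides planned dose by the actual duration of the first 4 cycles, so planned dose intensity is not the planned rate and its comparison with actual intensity cannot register late doses (minor, descriptive)

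*SAP*

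**What the plan says.** Among the exposure parameters in SAP 8.6.1 is dose intensity over Cycles 1 to 4, in a planned and an actual version, each "defined as total planned or actual dose from the first 4 cycles (mg) divided by actual duration of the first 4 cycles (weeks". One divisor serves both quantities.

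The Note under that line deals only with early withdrawal. After withdrawal for a reason other than progression or death, "the remaining cycles will be calculated with planned length, i.e., 3 weeks, and zero dose". After withdrawal for progression or death, "the number of cycles actually completed will be used". Neither rule replaces the length of a cycle that was delivered late.

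The same list contains "Dose compliance, defined as percentage of actual dose taken relative to planned dose", which has no time element, as well as duration of treatment and "Number of treatment infusions received". It closes with "Details of study treatment exposure will be listed for Safety Analysis Set".

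On the protocol side, treatment is every 3 weeks for the first 4 cycles (4.1.1). Section 4.4.1 states: "Dose reductions or dose escalations of AGEN1884 are not permitted". Delay is expected. Section 4.1.2 says "AGEN1884 administration will be delayed for the following adverse events (AEs", and 5.7.1 foresees that cycles may drift away from the scan schedule when therapy is delayed. Section 4.4.2 also foresees infusions not given in a cycle.

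**The concern.** A planned dose intensity should be a fixed reference: the planned dose over the planned time. Under SAP 8.6.1 it moves with the subject's own delays. Two things follow. The mg/week figure printed as planned is not the plan for any subject dosed late. And when planned and actual are set side by side, the time element that distinguishes dose intensity from dose compliance disappears.

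This is relevant here because reductions are barred, so late dosing is one of the main ways in which intensity can fall. At stake is how well one exposure table describes delivery of the assigned schedule. A reader who sees planned and actual intensity agree would take it that treatment was delivered at the intended rate.

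**Working it through.** The documents state no dose-intensity figure, so there is none to reproduce. The check applies the SAP definition directly.

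Inputs:
- Planned schedule: 4 cycles of 3 weeks = 12 weeks (Protocol 4.1.1).
- Phase 2 dose: 1 mg/kg (Protocol 3.1).
- Divisor: actual duration T for both quantities (SAP 8.6.1).
- Assumed, because not in the documents: body weight 70 kg (range 50 to 90 kg), total delay d in weeks, and the last cycle counted as 3 weeks.

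Formulas, with P = planned dose and A = actual dose:
- SAP planned intensity = P/T; SAP actual intensity = A/T.
- SAP comparison = (A/T)/(P/T) = A/P. T cancels.
- Planned rate = P/12.
- Delivery relative to plan = (A/T)/(P/12) = (A/P) × (12/T).

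Four full doses at 70 kg give P = A = 280 mg and T = 12 + d. The planned rate is 280/12 = 23.3 mg/week.

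| Delay d (weeks) | T (weeks) | SAP planned = SAP actual (mg/week) | SAP actual/planned | Delivery relative to plan, 12/T |
|---|---|---|---|---|
| 0 | 12 | 23.3 | 100% | 100% |
| 2 | 14 | 20.0 | 100% | 86% |
| 3 | 15 | 18.7 | 100% | 80% |
| 4 | 16 | 17.5 | 100% | 75% |
| 6 | 18 | 15.6 | 100% | 67% |

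The percentages do not depend on weight. In mg/week with d = 3, a 50 kg subject has a plan of 200/12 = 16.7 and an SAP planned figure of 200/15 = 13.3. At 90 kg the figures are 360/12 = 30.0 and 360/15 = 24.0.

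The Note does not rescue the comparison. Take progression after two cycles, the first lasting 6 weeks: T = 9. The SAP gives (2/9)/(2/9) = 100%, while delivery relative to plan is (2/9)/(2/6) = 67%.

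One further point in the Note is open: whether the zero dose for unreached cycles applies to actual dose only or also to planned dose. For a withdrawal not due to progression or death after two on-time cycles, with T = 12:
- planned dose kept at 4 doses: (2/12)/(4/12) = 50%;
- planned dose also set to zero for the two unreached cycles: (2/12)/(2/12) = 100%.

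Likewise, 3 doses in 12 weeks with one omitted gives 3/4 = 75% only if the omitted cycle keeps its planned dose. So whether the comparison registers withdrawals and omitted doses depends on an assumption the SAP does not settle. The cancellation of T does not depend on it.

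**The case against.** The SAP asks for no ratio, so part of the criticism is aimed at a comparison that the reader supplies. Actual mg/week, taken alone, does fall with delay. The exposure listing remains, and treatment duration, number of infusions and the percentage of events leading to dose hold in each immune-related cluster (SAP 8.6.2) give indirect signs. Nothing downstream uses planned dose intensity: adverse-event rates per month use exposure time, and the primary endpoint in SAP 4.4 does not name it.

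All of this stands, and it sets the size of the point. It does not answer the point. The planned figure is wrong as a statement of the plan even if no ratio is formed, and no other exposure parameter compares actual with planned timing.

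Three stronger readings are tempting, and the documents do not support them:
- A reader might infer that delay is lost from the report. It is not, for the reasons just given; only this comparison fails to show it.
- A reader might infer that one and the same hold would give different results depending on whether a site records it as a shifted or an omitted dose. Four doses in 15 weeks and three in 12 are different dosing courses, which a corrected measure would also separate (80% against 75%, if the omitted cycle keeps its planned dose). The case report form is not among the documents, so nothing shows that sites have such a choice.
- A reader might infer that the line simply duplicates dose compliance. Over the same cycles and with the same planned dose the ratio is algebraically the same, but dose compliance carries no 4-cycle limit and no early-withdrawal rule.

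**Conclusion.** The definition is wrong as written, and the consequence is minor. For any subject dosed late in the first 4 cycles, planned dose intensity is understated: by 20% for a 3-week total delay and by 33% for 6 weeks. When all 4 doses are given in full, the planned/actual comparison reads 100% whatever the delay, against delivery of 86%, 80%, 75% or 67% of the planned rate for 2, 3, 4 or 6 weeks.

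The percentages rest on counting the last cycle as 3 weeks; the mg/week figures rest also on the assumed weights. How often Phase 2 doses were late is not in the documents, so no effect on the cohort summary is claimed. There is also no basis for inferring that any safety conclusion changes: the tables of adverse events, discontinuations and deaths do not use this quantity.

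**What to change.** In SAP 8.6.1:
- Define planned dose intensity as planned dose divided by planned duration. Planned duration is 3 weeks times the number of cycles counted under the existing Note: 4 cycles, or the cycles actually completed when withdrawal is for progression or death.
- Define planned dose as one full protocol-assigned dose for each counted cycle, including omitted cycles and cycles not reached after withdrawal for other reasons. State that the zero dose in the Note applies to actual dose only. Without this sentence the new planned figure could still depart from the plan.
- Keep actual dose intensity as actual dose divided by actual duration, and report actual over planned as relative dose intensity.
- State how Cycle 4 ends, for example Cycle 4 Day 1 plus 20 days. An on-time subject has Cycle 4 Day 1 on Day 64 and ends on Day 84. With the one-day addition in SAP 8.1, that is 84 − 1 + 1 = 84 days, or 12.0 weeks, and 100%.

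The cost is one definition and minor programming from dosing dates the SAP already uses. The downside is that relative dose intensity will read lower where doses were late, including shifts that are within protocol. The ±7-day window for Cycle 4 Day 1 in Protocol Table 10 alone gives 12/13 = 92% to 12/11 = 109%. A footnote should say that values modestly below 100% are not by themselves evidence of toxicity.
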